10.1.4 End of Treatment/Early Termination

The EOT/ET visit will occur at Week 52.

If a subject is permanently discontinued from the study, every attempt should be made to have the subject complete the ET assessments as described in Table 1. In the event a subject does not return to the clinical site for the ET visit, the Investigator must make every effort to contact the subject by telephone to discuss AEs, dosing compliance, and review concomitant medications, and the date of the last dose of study drug. In these cases, the collected information (AEs, concomitant medications, date of last dose of medication, etc.) via telephone will be documented in the site source documents and eCRF. Return of unused study drug and any other materials will be performed by courier where allowed.

10.1.5 Safety Follow-up Period/End of Study

For all subjects who complete the double-blind treatment period, a safety follow-up visit will occur at Week 56 (Visit 9), 4 Weeks (± 7 days) after the last dose of study drug.

Any unresolved AE or SAE will be followed according to Section 14.9.

10.1.6 Unscheduled Visits

An unscheduled visit is defined as any visit to the clinical site outside of the protocol specified time visits due to safety reasons or when a repeated measurement is required (e.g., obvious measurement errors, measuring device failure, confirmation of out-of-range results), where the subject is seen by study personnel.

At the discretion of the Investigator, if deemed necessary, additional unscheduled safety assessments such as routine blood sampling, dose reductions may be performed. All unscheduled visits and assessments performed during the unscheduled visits will be recorded in the source documents and eCRF.

11 STUDY PROCEDURES

All subjects must sign and date the Institutional Review Board (IRB)/Independent Ethics Committee (IEC) approved ICF before any study-specific procedures are performed. Refer to Section 17.2.1 for further details.

All study procedures will be performed per the Schedule of Activities in Table 1.

11.1 Demographics and Other Baseline Characteristics

Demographic data will include year of birth, age, sex, body weight, body mass index, height, ethnicity*, and race*.

*where local law permits

11.2 Medical and Surgical History

Medical/surgical history before the screening period will include but not limited to medication, smoking, alcohol, psychiatric disease, and surgical history. In addition, history of hepatic injury (e.g., viral hepatitis, autoimmune hepatitis, nonalcoholic steatohepatitis, hypoxic/ischemic hepatopathy, biliary tract disease) will be recorded.

11.3 Prior and Concomitant Medication

Any prior medication, including prescription and over-the-counter medications, taken within 30 days before screening and all SSc-related medications used since diagnosis will be recorded on the eCRF and source documents. The following information will be collected: name of medication, dose, duration, and reason for use.

Concomitant medication(s) is defined as any medication, other than study drug, which is taken during the study, including prescription, over-the-counter medications, herbals, dietary supplements, and recreational drugs. All concomitant medication(s) taken while the subject is participating in the study will be recorded.

Concomitant medication(s) will be provided only if deemed necessary by the Investigator or the subject's personal physician.

Follow restrictions regarding concomitant medications are described in Appendix 2.

11.3.1 Treatments for Systemic Sclerosis

Apart from nintedanib that was recently approved for the treatment of SSc-ILD, no other drugs are approved for the treatment of SSc, and no adequate and well-controlled studies have demonstrated substantial evidence of a treatment effect in this disease. In the absence of approved drugs, evidence-based, consensus-derived recommendations to help guide treatment for subjects with SSc have been developed by the EULAR and European League Scleroderma Trials and Research (EUSTAR) group, a group of experts from the US and the European Union.²⁵ The EUSTAR consensus statement includes 16 recommendations for the treatment of organ-specific complications. The actual recommendations are aimed to guide pharmacological treatment of SSc-specific organ involvement. These recommendations are not meant to replace the physician's clinical judgement or the patient-physician shared decision. With respect to skin involvement, EUSTAR recommends that methotrexate may be considered for treatment of skin manifestations of early dcSSc but notes that no positive effects on other organ manifestations have been established for methotrexate. Despite its known toxicity, EULAR recommends

treatment of SSc-ILD using cyclophosphamide. Other recommended treatments include autologous stem cell transplant.²⁵

Treatment with investigational agents, cell-depleting therapy or bone marrow transplantation, ultraviolet (UV) phototherapy, cyclophosphamide, rituximab, or cyclosporine, Small molecules such as JAK inhibitors (e.g., tofacitinib), pirfenidone, tocilizumab, TNF Inhibitors (etanercept, infliximab, certolizumab, golimumab, adalimumab) and abatacept are prohibited during the study (Section 9.4).

Patients will be allowed to receive rescue therapy for worsening of skin thickening and/or deterioration of FVC and/or other scenarios, as described below (Section 11.3.1.2).

Concomitant therapies for treatment of other SSc complications and disease manifestations are permitted as described in Sections 11.3.1.1 and 11.3.1.3. It is important that dose regimens of medications taken by patients during the double-blind treatment period (through Week 52) remain stable if intended for chronic use. However, dose adjustments for such medications will be allowed as required for patient safety, after discussion with the Medical Monitor.

Concomitant treatments other than those described below (Sections 11.3.1.1 and 11.3.1.3) may be initiated for management of SSc complications after discussion with the Medical Monitor.

11.3.1.1 Medications Commonly Used in Systemic Sclerosis

NSAIDs and Analgesics

Patients may be treated with NSAIDs, including cyclooxygenase-2 (COX-2) inhibitors during the study. The dose of NSAIDs should remain stable through Week 52, unless dose reduction is required for patient safety. The choice and doses of NSAIDs are at the discretion of the Investigator. For patients who receive corticosteroids and/or NSAIDs, prophylactic treatment with proton-pump inhibitors or H2-receptor blockers may be added at the Investigator's discretion, according to local standard of care. Analgesics up to the maximum recommended dose may be used as required to treat pain. However, patients should be discouraged from using analgesics, including NSAIDs, within 12 hours prior to performance of efficacy assessments at every clinic visit.

Oral, Intravenous, or Intramuscular Corticosteroids

Subjects may receive corticosteroids at a stable dose of ≤ 10 mg/day of prednisone or equivalent during the study. Increases in corticosteroid doses for chronic treatment of SSc are not allowed during the study. To treat non-SSc-related conditions, doses of oral corticosteroids up to ≤ 40 mg/day of prednisone (or equivalent) are permitted for 2 weeks. The dose of the corticosteroid should be tapered down to the previous level as rapidly as medically possible. Decreases in corticosteroid doses for safety reasons are permitted.

DMARDs/Immunosuppressive Agents

All conventional Disease-modifying anti-rheumatic drugs (DMARDs)/Immunosuppressive agents, except for the permitted Immunosuppressant Therapy listed below, must be discontinued with appropriate washout prior to the initiation of study drug as described in the Exclusion criteria (Section 9.4) and are prohibited during the study, except when given as rescue therapy as described in Section 11.3.1.2 or for other significant systemic sclerosis complications as described in Section 11.3.1.3.

Permitted Immunosuppressant Therapy

Only one of the following immunosuppressant therapy is allowed during the study. Switching and addition of an immunosuppressant therapy is not allowed during study treatment (see Section 9.4) except when given as rescue therapy as described in Section 11.3.1.2.

- Mycophenolate (up to 3 g/day)
- Mycophenolic acid (up to 2.14 g/day)
- Methotrexate (up to 25 mg/Week)
- Leflunomide (up to 20 mg/day)
- Azathioprine (up to 3 mg/kg/day)

Vaccine

During study treatment, subject is allowed to receive non-live (inactivated) vaccines, such as some of the seasonal flu vaccines (Influenza) and Pneumovax vaccines. Subjects on any immunosuppressant therapy will need to hold their therapy per local guidelines, if they plan to receive any live or live-attenuated vaccines such as Covid-19 vaccine once it becomes available.

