 - c. Pirfenidone received within 12 weeks prior to screening.
 - d. Infliximab, certolizumab, golimumab, adalimumab, abatacept, tocilizumab within 10 weeks prior to screening.
 - e. Etanercept within 4 weeks prior to screening.
 - f. Oral, intravenous, or intramuscular corticosteroids (prednisone > 10 mg/day or equivalent) received within 30 days prior to screening.
 - g. Nintedanib within 12 weeks prior to screening.
 - h. More than 1 of the immunosuppressant therapy listed below as concomitant therapy with study drug, has changed one of the medications below within 12 weeks prior to screening, or not on a stable dose of the same medication for at least 12 weeks prior to screening.
 - i. Mycophenolate (up to 3 g/day), or
 - ii. Mycophenolic acid (up to 2.14 g/day), or
 - iii. Methotrexate (up to 25 mg/Week), or

- iv. Leflunomide (up to 20 mg/day), or
- v. Azathioprine (up to 3 mg/kg/day).

21. Treatment with afamelanotide or other MC1R agonist within 12 weeks before screening (Visit 1).
22. Treatment with any drugs or supplements which, in the opinion of the Investigator, may interfere with the objectives of the study or safety of the subject.
23. Has previously exposed to MT-7117 (this does not include placebo treated subjects).
24. Has previously treated with any investigational agent within 12 weeks prior to screening OR 5 half-lives of the investigational product (whichever is longer).
25. Female subjects who are pregnant, lactating, or intending to become pregnant during the study.
26. [REDACTED]
27. Has a positive autoantibody status of anti-centromere antibody.

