16.1 Determination of Sample Size

The planned sample size of 72 is expected to provide power for the comparison between MT-7117 treatment group and placebo group for ACR CRISS score at Week 52. The calculation of sample size assumes a 2-sided alpha level of 0.05 and uses EAST (Version 6.5) for Wilcoxon Mann Whitney test. The randomized 72 subjects (36 subjects for MT-7117 and 36 subjects for placebo) with a 1:1 allocation ratio would provide 80% power to detect treatment difference of 0.35 (35% improvement on MT-7117 treatment group compared to placebo group) in ACR CRISS score at Week 52 with an associated standard deviation (SD) of 0.5.

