8.1.8 Rescue Medications

The Rescue Medications will be summarized and listed on the SAF population. The data will be coded using World Health Organization Drug Dictionary (WHO-DD). The summaries will be by ATC level 2 and preferred name and period and treatment. The Rescue Medications and the reason (e.g., Worsening mRSS of a minimum of 5 points and at least 25% increase relative to baseline) to use it will be summarized by Placebo, MT-7117 over all, MT-7117 [REDACTED] only, [REDACTED] to [REDACTED] regimen, [REDACTED] to [REDACTED] regimen.

[Analysis period using the start date of the rescue medication]

Week 16 =< Period =< Week 26

Week 26 < Period =< Week 39

Week 39 < Period =< Week 52

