8.2.1 Primary Efficacy Endpoint

Primary Analysis

The primary treatment comparisons of interest are the ACR CRISS score for MT-7117 treatment group compared with placebo group at Week 52. MT-7117 treatment group includes all subjects treated with MT-7117 regardless down titrated or not. The treatment MT-7117 dose level at EOT will be compared with placebo as secondary analysis.

The primary endpoint will be summarized using descriptive statistics with interquartile range. The distribution of ACR CRISS score may not be normal distribution. For ACR CRISS score at Weeks 16, 26, 39, and 52 the comparison between MT-7117 treatment group and placebo group will be performed using the non-parametric analysis method. The point estimates and 2 sided 95% CIs and associated P-values for the difference between the treatment groups will be obtained using the Hodges-Lehman estimator corresponding to Wilcoxon's rank sum test. This non-parametric analysis will be performed with multiple imputation method, assuming missing at random. A supportive analysis will be performed at the same way for the primary endpoints using the per-protocol set (PPS). As a secondary analysis for the primary endpoint, the same analysis method will be applied to the intent to treat (ITT) population but the patients' data after taking rescue therapy will not be included. This approach will be performed to investigate a sensitivity for the primary analysis.

MI Step 1: The ACR CRISS score at week 52 will be multiply imputed using Fully Conditional Specification Method methodology under MAR assumption. The imputation for the missing ACR CRISS total score at week 52 will be conducted using all visit data of all subjects with available ACR CRISS total score up to week 52. The 50 different imputed datasets will be created using the MI procedure in SAS with 2023 for seed value. The following factors will be included in the imputation model: treatment group (TRT01P), randomization strata (the baseline autoantibody status of anti-RNA Polymerase III (positive or negative)).

[REDACTED]

[REDACTED]

[REDACTED]

[REDACTED]

[REDACTED]

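### Protocol 11.3.1.1 contradicts itself on non-rescue immunosuppressants and no section names nintedanib as barred on study, so the SAP's rescue-excluded analysis can keep outcomes under newly started SSc treatment

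*Protocol*

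**What the plan says.** **Rescue.** Protocol 11.3.1.2 opens rescue at Week 16 for confirmed %pFVC decline and at Week 26 for skin worsening. It sends other serious worsening to the Medical Monitor.

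**Immunosuppressants.** Protocol 11.3.1.1 has two adjoining paragraphs. The first prohibits conventional DMARDs and immunosuppressive agents on study, apart from five permitted background agents, "except when given as rescue therapy as described in Section 11.3.1.2 or for other significant systemic sclerosis complications as described in Section 11.3.1.3". The second covers the five permitted agents and states: "Switching and addition of an immunosuppressant therapy is not allowed during study treatment", with rescue as its only exception.

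**Other SSc treatment.** Protocol 11.3.1 says that concomitant treatments beyond those described "may be initiated for management of SSc complications after discussion with the Medical Monitor". Section 11.3.1.3 asks for the same discussion unless the need is urgent, and leaves out therapies prohibited by 11.3.1. Neither gives an earliest week.

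**Nintedanib.** Exclusion 20g in Protocol 9.4 reads "Nintedanib within 12 weeks prior to screening". The on-study list in 11.3.1 refers back to 9.4 and also covers cyclophosphamide, rituximab and cyclosporine. It continues: "Small molecules such as JAK inhibitors (e.g., tofacitinib), pirfenidone, tocilizumab, TNF Inhibitors (etanercept, infliximab, certolizumab, golimumab, adalimumab) and abatacept are prohibited during the study". Pirfenidone is there and nintedanib is not. The Appendix 2 tables do not name nintedanib either.

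**SAP.** Section 8.2.1 plans a secondary analysis of the primary endpoint in the ITT population in which subjects' "data after taking rescue therapy will not be included". Its stated purpose is to examine the sensitivity of the primary result. The first period of the rescue table in SAP 8.1.8 is "Week 16 =< Period =< Week 26".

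**The concern.** The rescue-excluded analysis is meant to show whether the primary result depends on outcomes recorded while subjects were on another active SSc treatment. Its trigger is the rescue label, not the treatment. If a disease-modifying drug can be started for an SSc complication without that label, the subject's later mRSS, %pFVC, global assessments, HAQ-DI and CRISS stay in the analysis as outcomes of the randomised arm.

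If such starts were more common on placebo, the arm difference in this analysis would shrink. If they were more common on MT-7117, it would grow. In either case, agreement between this analysis and the primary one would say less than it appears to.

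**Working it through.** **1. Which drugs could come in without the rescue label**

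| Agents | Governing text | Status outside rescue |
|---|---|---|
| Named in 11.3.1 (cyclophosphamide, rituximab, cyclosporine, JAK inhibitors, pirfenidone, tocilizumab, TNF inhibitors, abatacept) | Prohibited on study; 11.3.1.3 excludes them | Barred |
| Five permitted agents (mycophenolate, mycophenolic acid, methotrexate, leflunomide, azathioprine) | Second paragraph of 11.3.1.1 bars addition or switch; the first sets them apart before giving its exceptions | At most contradictory, not a permission |
| Conventional DMARDs or immunosuppressants on neither list | First paragraph allows them for SSc complications; second, read generally, does not | Contradictory |
| Nintedanib | Excluded for prior use only; not on the 11.3.1 list or in the Appendix 2 tables | Not named as barred |

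The Appendix 2 tables concern drug interactions and are not exhaustive. That is a further reason to state nintedanib's status outright.

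**2. Timing.** Labelled rescue can cover at most 52 − 16 = 36 weeks (FVC) or 52 − 26 = 26 weeks (skin). The complications route gives no start week. Protocol 8.1 holds skin and other scenarios to Week 26, so an earlier start for a complication would tend to be recorded as a concomitant treatment.

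**3. What the SAP does with such a start**
- 8.2.1: only rescue removes data.
- 8.1.8: the rescue table begins at Week 16.
- 8.1.7: the prohibited-medication table is built from Appendix 2, whose tables list neither nintedanib nor the five agents.
- 8.1.6: dose and duration of the five agents and corticosteroids are summarised, including drugs started after first dose, with no consequence for efficacy data.
- 5.3 and 7.1.1.1: the per-protocol set removes subjects with major deviations. Taking prohibited medication is one, but a drug accepted under 11.3.1.3 does not meet that description by rule.

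**4. The plan's power figure.** Protocol 16.1 gives 36 + 36 = 72 subjects, a difference of 0.35, an SD of 0.5 and 80% power for a Wilcoxon-Mann-Whitney test. It also states: "The calculation of sample size assumes a 2-sided alpha level of 0.05". Noether's formula gives:
- P(X>Y) = Φ(0.35 / (0.5 × √2)) = 0.6897
- N = (1.960 + 0.842)² / (3 × 0.1897²) = 72.7
- Power at N = 72: Φ(√(3 × 72) × 0.1897 − 1.960) = 79.6%

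Simulation on normal data gives 81.6%. The 80% is reproduced.

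**5. Scale, by assumption only.** The documents give no rate of non-rescue treatment. Suppose a share f of placebo subjects start one and gain the full 0.35, the SD is unchanged and all data are kept. The difference becomes 0.35 × (1 − f):

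| f | Placebo subjects (36 × f) | Difference | Power, N = 72 |
|---|---|---|---|
| 0 | 0 | 0.350 | 79.6% |
| 5% | about 2 | 0.3325 | 75.8% |
| 10% | about 4 | 0.315 | 71.5% |
| 20% | about 7 | 0.280 | 61.9% |
| 30% | about 11 | 0.245 | 51.3% |

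A smaller gain dilutes less, and starts mainly on MT-7117 would act the other way.

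For one subject, the CRISS equation weights %pFVC change by 0.21. If the added drug preserved 3 to 5 points (assumed), the logit would rise by 0.63 to 1.05. A score of 0.50 would become 0.65 to 0.74, and 0.30 would become 0.45 to 0.55.

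**The case against.** The strongest reply is that treatment for worsening disease mostly goes through rescue already. Section 11.3.1.2 covers skin, FVC and other serious scenarios, and nintedanib started for confirmed FVC decline from Week 16 would be rescue, with later data dropped. A washout at entry and an on-study list are different rules, so their mismatch on nintedanib need not be an error. Starting the rescue table at Week 16 matches the earliest permitted rescue. These points stand, and they narrow the number of cases. They do not cover a start before Week 16, or one recorded as treatment of a complication.

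The SAP also has other tools. The list of major deviations is a minimum, and the blinded review may add any deviation that could influence the primary endpoint, so the per-protocol analysis may catch some cases. That depends on a classification not yet made, and it removes whole subjects rather than data after the start. The prespecified subgroups by concomitant mycophenolate or immunosuppressant describe use and do not handle the data that follow a start.

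A reader might infer that new immunosuppressants may be started freely from Day 1. The documents do not support that. The agents listed in 11.3.1 stay barred, adding one of the five permitted agents is at most a contradiction, and Day 1 is only an inference from a missing time limit. The route also requires a significant SSc complication and a Medical Monitor discussion unless urgent.

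**Conclusion.** The protocol text conflicts on whether an immunosuppressant may be started outside rescue, and it leaves nintedanib's on-study status unstated. The rescue-excluded analysis would keep data collected under any such treatment, so it cannot fully do the job the SAP gives it.

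The reach is limited to that secondary analysis. A reader might conclude that the primary result is compromised. It is not changed by this gap, because the primary analysis has no rule that drops data after rescue or any other added treatment. Nor do the documents show false reassurance in a given direction, since the rate of use and its balance between arms are unknown. The power figures rest on assumed rates of 5% to 30% on placebo and an assumed gain of 0.35. They show how few subjects would matter at 36 per arm and are not a forecast. The point should be settled before unblinding.

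**What to change.** **SAP 8.2.1.** Define the event for this analysis as the first start of, or switch to, any new immunosuppressant, biologic or antifibrotic given for SSc (including nintedanib) after first dose, whether recorded as rescue or as concomitant medication. Identify cases by drug and start date at the blinded data review. Resolve incomplete start dates there too, because the imputation rules in SAP 7.1.1.4 were written only to decide concomitant use. Do not trigger on the dose adjustments that Protocol 11.3.1 allows for safety.

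**SAP 8.1.8.** Beside the rescue table, tabulate non-rescue starts by arm, including those before Week 16.

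**Protocol.** Exclusion 20g in 9.4 and Sections 11.3.1, 11.3.1.1, 11.3.1.2 and 11.3.1.3 must be reconciled, including nintedanib's on-study status. No view is given here on which clinical rule is right.

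**Cost.** The SAP change is wording plus a blinded review of medication records already being collected; the protocol clarification is a minor amendment. The statistical price is that a few more subjects have later data set to missing and imputed under missing at random. That assumption is hard to defend for subjects who are worsening. It is weakest for starts before Week 16, because the SAP reports CRISS only from Week 16, so those subjects would have no earlier score to inform the imputation. The tabulation lets readers see how much rests on it.

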11.3.1.2 Rescue Therapy

Subjects with worsening scleroderma such as skin thickening with worsening in mRSS of a minimum of 5 points and at least 25% increase relative to baseline will be allowed to use rescue therapy starting at or after Week 26.

At or after Week 16, rescue therapy will also be allowed with a decrease of > 10 relative percentage points in %pFVC compared with baseline, such a decline from baseline confirmed on two separate occasions within a 4-week period (after 2 separate confirmations within 4 weeks via an unscheduled visit).

Initiation of rescue therapy will be based on Investigator's clinical judgment and should be discussed with the Medical Monitor(s).

For worsening of skin thickening at or after Week 26, immunosuppressive therapies (methotrexate, mycophenolate mofetil and others) may be used as rescue therapy after discussion with the Medical Monitor.

For worsening FVC at or after Week 16, treatment of SSc-related ILD should be initiated as indicated by local treatment guidelines. The choice of rescue therapy for worsening FVC should be discussed with the Medical Monitor prior to initiation of treatment.

For other scenarios related to worsening scleroderma such as involving organ impairment or life-threatening or debilitating disease manifestations, the Investigator should contact the Medical Monitor(s).

Start date, reason and use of rescue therapy during the double-blind treatment period will be documented in the eCRF.

The subjects who initiate rescue therapy will be allowed to continue taking study drug in order to complete study treatment to Week 52. Only one rescue therapy can be added during the study treatment. A change in rescue therapy is permitted after discussion with the Medical Monitor

and Sponsor. The analysis using the subject's data after taking rescue therapy is described in the Section 16.3.4.1.

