9.3 Inclusion Criteria

Subjects who meet all the following criteria will be considered eligible to participate in the study:

1. Must provide signed and dated informed consent form (ICF) to participate in the study. Subjects must be able to (in the judgment of the Investigator) understand the nature of the study and all risks involved with participation in the study. Subjects must be willing to cooperate and comply with all protocol restrictions and procedures including study visits.
2. Male or female age ≥ 18 years at screening with documented diagnosis of SSc, as defined using the 2013 ACR/European League Against Rheumatism (EULAR) criteria (Appendix 1).
3. Has diffuse cutaneous form of SSc according to LeRoy and Medsger's criteria (Appendix 1).
4. Disease duration ≤ 5 years from the first non-Raynaud's phenomenon manifestation.
5. Has an mRSS of 15 to 45 units at screening and have clinical skin involvement proximal and distal to the elbows, knees, or both or any truncal involvement, with or without face involvement.
6. If disease duration is > 24 months defined as time from the first non-Raynaud phenomenon manifestation, subject must fulfil at least 1 of the criteria listed below that are indicative of active disease at screening:
 - a. A documentation of new skin involvement that occurred within the past 9 months, or
 - b. Increase in mRSS ≥ 3 units within the past 9 months, or
 - c. Presence of tendon friction rubs (TFRs) or,
 - d. C-reactive protein ≥ 6 mg/L, or
 - e. Erythrocyte sedimentation rate ≥ 28 mm/hr, or
 - f. Platelet count $\geq 330 \times 10^9/L$ (330,000/microliter).

NOTE: Investigator should exclude all other acute intercurrent illness if subjects fulfilling laboratory criteria (d, e, f) only.

7. Willing to follow restrictions regarding concomitant medications that are described in Appendix 2.

8. Female subjects who are non-lactating and have a negative urine pregnancy test at baseline visit prior to receiving the first dose of study drug.
9. Female subjects of childbearing potential and male subjects with partner of childbearing potential currently using/willing to use 2 effective methods of contraception including barrier method as described in Appendix 3.

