10.1.3 Double-blind Treatment Period

Subjects who successfully complete the screening period will return to the clinical site on Day 1 of the double-blind treatment period to reconfirm his/her eligibility by reviewing the inclusion and exclusion criteria (Table 1) and evaluate other baseline criteria prior to randomization. To be randomized into the double-blind treatment period, the subject must meet the required criteria at screening and at baseline. Eligible subjects will be randomized, and study drug administration will begin on Day 1 (Visit 2) after confirmation of all baseline criteria.

Study visits will occur at the study site per the Schedule of Activities (Table 1).

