The Physician Global Assessment is used to assess the physician's rating of overall health of the subject. Physicians rate the perceived health of the subject on an 11 point

scale from 0 (excellent) to 10 (extremely poor). Higher scores indicate worse disease in terms of severity, damage, or overall disease, but there is no standardization for the scale (Pope 2011). A negative change from baseline indicates improvement. Expert consensus has suggested a range of 8-13 units on Global VAS scale 100 mm. for the MCID (Gazi et al. 2007). Therefore, -0.8 to -1.3 points will be defined as MCID in this assessment.

- Modified Rodnan Skin Score (MRSS)

The mRSS will be assessed by a qualified and trained Efficacy Assessor to limit the variability. The same Efficacy Assessor will measure skin thickness on 17 different body areas on a scale from 0 (normal) to 3 (severe). Global average scoring method (The assessor scores individual sub-areas, as needed for differences within large areas and takes average of sub-areas to attain the score for that overall area) will be used as a scoring technique in this study. Worsening of skin fibrosis as measured by the mRSS score was associated with a disease progression and overall mortality in subjects with dcSSc, indicating that the mRSS is a good surrogate marker for disease progression. The mRSS is a measure of skin thickness across 17 different body sites and has a range of 0 to 51 in whole units. Total score is derived from the sum of the 17 different body areas. If at least one domain score is missing, the total score will be regarded as missing. The MCID has been reported by Dinesh Khanna 2019 to be 3 to 5 units for dcSSc patients.

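### The numeric skin rescue criterion (at least +5 points and at least +25%) cannot be met from eligible baseline mRSS 41 to 45, because the scale stops at 51

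*Protocol*

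**What the plan says.** Protocol 11.3.1.2 lets a subject start rescue therapy at or after Week 26 for worsening scleroderma, and illustrates this with skin thickening defined as "worsening in mRSS of a minimum of 5 points and at least 25% increase relative to baseline". Both parts are required. SAP 8.1.8 gives the same numbers as an example of a reason to be tabulated: "Worsening mRSS of a minimum of 5 points and at least 25% increase relative to baseline".

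Three other provisions fix the range in which this rule operates:

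- Protocol 9.3, criterion 5: "Has an mRSS of 15 to 45 units at screening".
- Protocol 10.1.3: to be randomized, "the subject must meet the required criteria at screening and at baseline".
- SAP 7.1.2.2: the mRSS "has a range of 0 to 51 in whole units". This agrees with Protocol 11.6.1, which scores 17 areas from 0 to 3.

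Neither document gives a cap, an exception or another skin number for high baselines. The synopsis and Protocol 8.1 mention skin rescue without any number.

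**The concern.** A relative threshold on a bounded scale stops working once the baseline is close enough to the ceiling. Here that happens inside the plan's own entry range. A subject who goes from 20 to 25 meets the criterion. A subject who goes from 42 to 51, a 9-point rise to the worst possible score, does not. SAP 7.1.2.2 cites a minimal clinically important difference of 3 to 5 units for mRSS. The rises still possible from 41 to 45 (10 down to 6 points) exceed that range and still do not qualify.

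The threshold matters because Protocol 11.3.1.1 states that "Switching and addition of an immunosuppressant therapy is not allowed during study treatment", except as rescue under 11.3.1.2, and this is the only skin number in that section. For a subject at 41 to 45 whose skin worsens, the site cannot apply the stated rule in full. The tabulated reason quoted from SAP 8.1.8 would not describe that subject either.

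**Working it through.** **Inputs.** Rescue rule: at least +5 points and at least +25% (Protocol 11.3.1.2). Eligible mRSS: 15 to 45 (Protocol 9.3, reconfirmed at baseline under 10.1.3). Scale maximum: 51, whole units (SAP 7.1.2.2).

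**Plan's own figure.** 17 areas × 3 = 51, which reproduces the stated maximum.

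**Score required.** For baseline b, the required total is max(b + 5, 1.25b rounded up to a whole unit). The 5-point part governs up to b = 20, where both parts give 25. Above that the 25% part governs.

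**Highest baseline that can qualify.** 1.25b ≤ 51 gives b ≤ 51/1.25 = 40.8. The break therefore falls between 40 and 41 and does not depend on rounding the required score.

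| Baseline | 1.25 × baseline | Score needed | Attainable (≤ 51)? | Largest possible rise |
|---|---|---|---|---|
| 39 | 48.75 | 49 | yes | 12 (30.8%) |
| 40 | 50.00 | 50 | yes | 11 (27.5%) |
| 41 | 51.25 | 52 | no | 10 (24.4%) |
| 42 | 52.50 | 53 | no | 9 (21.4%) |
| 43 | 53.75 | 54 | no | 8 (18.6%) |
| 44 | 55.00 | 55 | no | 7 (15.9%) |
| 45 | 56.25 | 57 | no | 6 (13.3%) |

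Every whole-number baseline from 15 to 40 can satisfy both parts. The five from 41 to 45 cannot, out of 45 − 15 + 1 = 31 eligible scores.

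**Which part fails.** Adding 5 to 41, 42, 43, 44 and 45 gives 46, 47, 48, 49 and 50, all within the scale. Only the percentage part is out of reach.

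**Check of the proposed rule** (at least +5, and either at least +25% or a total of at least 50). For b ≤ 40, 1.25b ≤ 50, so the alternative is never easier than the 25% part and every threshold stays the same. For b = 41 to 45, b + 5 ≤ 50, so the threshold is 50: rises of 9, 8, 7, 6 and 5 points, or 9/41 = 22.0%, 8/42 = 19.0%, 7/43 = 16.3%, 6/44 = 13.6% and 5/45 = 11.1%. The required score never falls as baseline rises (49 at 39, then 50 from 40 to 45).

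**The case against.** The strongest reply is that Protocol 11.3.1.2 already deals with this. The number follows wording that marks it as an example. Every rescue start rests on the Investigator's judgment with Medical Monitor discussion. A later sentence in the same section allows immunosuppressants for worsening skin from Week 26, after that discussion, without restating a threshold. The FVC route from Week 16 does not depend on mRSS, and a separate route covers other serious manifestations. Protocol 11.3.1.1 and 11.3.1.3 also provide for treatment of other significant complications. SAP 8.1.8 offers the number only as an example.

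All of this stands, and it rules out a stronger reading. A reader might infer that subjects at 41 to 45 are shut out of rescue, or that sites have nothing numeric to go on. The documents support neither: the routes above are open, and the 5-point part can still be applied. It would also be speculation to say that sites would decide differently, since the same judgment step applies at every baseline.

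The flexibility softens the consequence but does not make the stated threshold attainable. A further fair objection is that 50 is a choice not found in the documents, and that what counts as worsening near the ceiling is a clinical question. That also stands: 50 is proposed because it continues the existing threshold at baseline 40 without a jump.

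**Conclusion.** The point holds as a minor error of arithmetic. The numeric skin criterion cannot be met from baseline 41 to 45, so subjects with the most extensive skin disease cannot qualify on it even at the maximum score. This rests on reading the two parts as jointly required, as the text does, and on 45 as the highest baseline. If a baseline above 45 were accepted, the gap would be wider.

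The number of subjects cannot be derived, because neither document gives a baseline mRSS distribution. The 5 of 31 eligible scores must not be read as a share of the 72 subjects. Only those at 41 to 45 whose skin then worsens from Week 26 matter, so the number is probably very small.

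A reader might also infer that the power or the primary analysis is at fault. The sample-size inputs do not involve this rule, and the analysis method does not change. Nor is the effect strictly confined to the sensitivity analysis that omits post-rescue data. Protocol 16.3.4.1 and SAP 8.2.1 exclude those data only there, so the primary analysis appears to keep them. A rescue decision could therefore alter that subject's Week 52 ACR CRISS score.

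**What to change.** Amend the skin rule in Protocol 11.3.1.2 to: *an increase in mRSS of at least 5 points and either at least 25% relative to baseline or a total mRSS of 50 or more*. Put the same text in SAP 8.1.8.

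The downside is a lower relative bar at 41 to 45, as shown in the working, so skin rescue becomes slightly easier there. The clinical team should confirm that 50 is acceptable.

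Because this changes access to treatment, it needs a Protocol Modification under Protocol 17.2.2, with notice to regulatory authorities and ethics committees. It does not justify one alone and should go into the next one. It adds no visits or assessments. Whether the eCRF repeats the criterion cannot be seen from the documents and should be checked at the same time.
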